9.1.6 Unscheduled Visits

Visits to the research site for **other reasons** than dressing changes may be captured as an Unscheduled Visit at the discretion of the Investigator with all information recorded in the source documents and on the Unscheduled Visit CRF.

9.1.7 Concomitant Medications and Therapies

A concomitant treatment is any drug, substance or device administered at any time from enrolment into the study through the last study visit.

9.1.7.1 Concomitant Medications

9.1.7.1.1 Excluded Concomitant Medications

- Oxidizing agents such as hypochlorite solutions (e.g. EUSOL) or hydrogen peroxide in conjunction with AGB, as these can reduce the absorbency of the dressing.

9.1.7.1.2 Recording Concomitant Medications in the CRF

Concomitant medications meeting the following criteria will be recorded on the CRF:

- All current and past reference wound medication.
- Concomitant medication used to treat the reference wound and the peri-wound area (such as treatment for erythema, irritation, itching), together with the indication for the medication.
- Concomitant medications used to treat all Adverse Events (AE), Serious Adverse Events (SAE), ADE, Serious Adverse Device Effects (SADE) and Unanticipated Serious Adverse Device Effects (USADE).

CONFIDENTIAL AND PROPRIETARY

This document contains information that is confidential and proprietary to Smith & Nephew PLC and Smith & Nephew, Inc. and is intended for use only by Smith & Nephew and its manufacturer. It shall not be reproduced or copied in whole or in part, nor shall the contents be disclosed by any means without prior written permission from Smith & Nephew, nor shall anyone make any use of it that is contrary to the expressed or implied wishes of Smith & Nephew.

| | |
|--|---|
| Study Protocol—Device |  |
| A Prospective, Multi-center, Post-Market Clinical Follow-Up Study to Evaluate the Safety and Effectiveness of ALLEVYN Gentle Border | Number: ALLEV.PMCF.2017.13 |
| | Version: 3.0 |
| | Date: 21 JUN 2019 |
| | Page: Page 40 of 90 |

9.1.7.2 Concomitant Therapies

9.1.7.2.1 Therapies Prohibited During the Study

- Negative pressure wound therapy during the study (e.g. PICO)

9.1.7.2.2 Recording Concomitant Therapies in the CRF

Concomitant therapies meeting the following criteria will be recorded on the CRF:

- All current and past reference wound therapies.
- Concomitant therapies used to treat the reference wound and the peri-wound area, together with the indication for the therapy.
- Concomitant medications used to treat all Serious Adverse Events (SAE), ADE, Serious Adverse Device Effects (SADE) and Unanticipated Serious Adverse Device Effects (USADE). Adverse device effects related to administration of these treatments must be documented in the appropriate CRF.

9.1.8 Discontinued Subjects

Discontinued subjects are those who voluntarily discontinue participation in the study, who are withdrawn from the study for reasons of safety or non-compliance, or who are withdrawn from the study for failure to complete the patient scores at Visit 1. Where possible, the Treatment Discontinuation CRF should be completed for all subjects who discontinue the study early. When consent is withdrawn, the date of and reason for discontinuation should be captured.

Subjects may be withdrawn from the study at any time if, in the opinion of the Investigator, their continued participation in the study poses a risk to the subject, as outlined in section 7.8.1.

If appropriate, the Investigator will advise the subject of subsequent therapy and/or procedures necessary for their medical condition, which will consist of standard care.

CONFIDENTIAL AND PROPRIETARY

This document contains information that is confidential and proprietary to Smith & Nephew PLC and Smith & Nephew, Inc. and is intended for use only by Smith & Nephew and its manufacturer. It shall not be reproduced or copied in whole or in part, nor shall the contents be disclosed by any means without prior written permission from Smith & Nephew, nor shall anyone make any use of it that is contrary to the expressed or implied wishes of Smith & Nephew.

| | |
|--|---|
| Study Protocol—Device |  |
| A Prospective, Multi-center, Post-Market Clinical Follow-Up Study to Evaluate the Safety and Effectiveness of ALLEVYN Gentle Border | Number: ALLEV.PMCF.2017.13 |
| | Version: 3.0 |
| | Date: 21 JUN 2019 |
| | Page: Page 41 of 90 |

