| Informed Consent | √ | | | | | | |
| Demographics/ Medical History | √ | | | | | | |
| Verify Inclusion/ Exclusion Criteria | √ | | | | | | |
| Allocate Study ID Number | √ | | | | | | |
| Concomitant Medication | √ | √ | √ | √ | √ | √ | √ |
| CWIS Patient Questionnaire | √ | √ | √ | √ | √ | | √ |
| Patient Pain Scale | √ | √ | √ | √ | √ | √ | |
| Patient Assessment | | √ | √ | √ | √ | √ | |
| Wound Assessment | √ | √ | √ | √ | √ | √ | √ |
| Photograph Dressing in situ Before Removal | | √ | √ | √ | √ | √ | √ |
| Dressing Change | | √ | √ | √ | | √ | |
| Photograph Wound Before Dressing Application | √ | √ | √ | √ | √ | √ | √ |
| Dressing Performance | √ | √ | √ | √ | √ | √ | |

CONFIDENTIAL AND PROPRIETARY

This document contains information that is confidential and proprietary to Smith & Nephew PLC and Smith & Nephew, Inc. and is intended for use only by Smith & Nephew and its manufacturer. It shall not be reproduced or copied in whole or in part, nor shall the contents be disclosed by any means without prior written permission from Smith & Nephew, nor shall anyone make any use of it that is contrary to the expressed or implied wishes of Smith & Nephew.

| | |
|--|---|
| Study Protocol—Device |  |
| A Prospective, Multi-center, Post-Market Clinical Follow-Up Study to Evaluate the Safety and Effectiveness of ALLEVYN Gentle Border | Number: ALLEV.PMCF.2017.13 |
| | Version: 3.0 |
| | Date: 21 JUN 2019 |
| Page: Page 9 of 90 | |

| Schedule of Events | Key Visits | | | | | Other Visits | |
|---------------------------------|-----------------------|-----------------|------------------|------------------|-------------------------|--------------------------------|--|
| | Visit 1 (Baseline) | Visit 2 | Visit 3 | Visit 4 | End of Study Visit 5 | Routine Dressing Changes | Treatment Discontinuation (before end of study) |
| | Day 0 | Day 7 (+/-3) | Day 14 (+/-3) | Day 21 (+/-3) | Day 28 (+/-3) | | |
| Adverse Event (AE) Assessment | √ | √ | √ | √ | √ | √ | √ |
| Record Device Deficiencies (DD) | √ | √ | √ | √ | √ | √ | √ |
| End of Study /Exit Form | | | | | √ | | √ |

CONFIDENTIAL AND PROPRIETARY

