7.8 WITHDRAWAL

7.8.1 Withdrawal from Treatment

If a subject is withdrawn from study treatment the Treatment Discontinuation Case Report Form (CRF) needs to be filled out. However, the subjects will be followed up to the end of the study for safety assessments until day 28 (\pm 3 days).

Subjects may be withdrawn early from study treatment based on the decision of the investigator. This might include but is not limited to the following reasons:

- Closure of the reference wound
- Worsening condition of reference wound
- If the subject misses two (2) consecutive dressing changes/study visits, interrupting treatment for longer than seven (7) days
- A change in treatment that is clinically warranted
- An adverse event (AE)
- Concurrent illness
- Adverse device effects (ADE)
- Non-compliance (e.g. did not follow instructions)
- Lost to follow-up (LTFU)
- Any other significant reason identified by the Investigator

CONFIDENTIAL AND PROPRIETARY

This document contains information that is confidential and proprietary to Smith & Nephew PLC and Smith & Nephew, Inc. and is intended for use only by Smith & Nephew and its manufacturer. It shall not be reproduced or copied in whole or in part, nor shall the contents be disclosed by any means without prior written permission from Smith & Nephew, nor shall anyone make any use of it that is contrary to the expressed or implied wishes of Smith & Nephew.

| | |
|--|---|
| Study Protocol—Device |  |
| A Prospective, Multi-center, Post-Market Clinical Follow-Up Study to Evaluate the Safety and Effectiveness of ALLEVYN Gentle Border | Number: ALLEV.PMCF.2017.13 |
| | Version: 3.0 |
| | Date: 21 JUN 2019 |
| | Page: Page 32 of 90 |

Any subject that does not meet the minimum reference wound size requirement following wound size tracing at Visit 1 will be withdrawn. Subjects withdrawn from the study for this reason alone shall be replaced by enrolment of a new study subject. A new subject number will be assigned.

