9. STUDY PROCEDURES

9.1 VISITS AND EXAMINATIONS

9.1.1 Summary

All subjects receive the ALLEVYN Gentle Border study device at visit 1 (Baseline, day 0). In total, all subjects need to perform 5 key study visits between week 1 and week 4, as shown in table 1. The visit schedule is based on the 7 days of maximum dressing wear time of ALLEVYN Gentle Border. The key visit date is counted from Baseline (day 0) and usually occurs on the same weekday in the following week. If a dressing change is required between the key visits the subject should come to an interim on-site visit (Routine Dressing Change Visit). A routine dressing change assessment will then be performed and documented in the Case Report Form. Then the subject

CONFIDENTIAL AND PROPRIETARY

This document contains information that is confidential and proprietary to Smith & Nephew PLC and Smith & Nephew, Inc. and is intended for use only by Smith & Nephew and its manufacturer. It shall not be reproduced or copied in whole or in part, nor shall the contents be disclosed by any means without prior written permission from Smith & Nephew, nor shall anyone make any use of it that is contrary to the expressed or implied wishes of Smith & Nephew.

| | |
|--|---|
| Study Protocol—Device |  |
| A Prospective, Multi-center, Post-Market Clinical Follow-Up Study to Evaluate the Safety and Effectiveness of ALLEVYN Gentle Border | Number: ALLEV.PMCF.2017.13 |
| | Version: 3.0 |
| | Date: 21 JUN 2019 |
| | Page: Page 35 of 90 |

continues with the next study key visit, counted from Baseline. If a subject is withdrawn from AGB treatment prior to key visit 5, this subject is still regarded as an active study participant. He/she should continue to come to the study key visit to follow-up with patients' safety up to visit 5.

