18. END OF STUDY

The end of the study is defined as the last visit of the last subject undergoing treatment in the study. ALLEVYN Gentle Border is a commercially available product and therefore should be available to subjects after their participation in this study. Subjects may participate for a maximum total duration of 28 (\pm 3) days.

Should circumstances arise which require the termination of the entire study prior to its planned completion (e.g. safety concerns) or circumstances arise which mean the end of the participation of an individual site (e.g. departure of Investigator, non-compliance) then this will be undertaken according to the SOPs of the Sponsor.

CONFIDENTIAL AND PROPRIETARY

This document contains information that is confidential and proprietary to Smith & Nephew PLC and Smith & Nephew, Inc. and is intended for use only by Smith & Nephew and its manufacturer. It shall not be reproduced or copied in whole or in part, nor shall the contents be disclosed by any means without prior written permission from Smith & Nephew, nor shall anyone make any use of it that is contrary to the expressed or implied wishes of Smith & Nephew.

| | |
|--|---|
| Study Protocol—Device |  |
| A Prospective, Multi-center, Post-Market Clinical Follow-Up Study to Evaluate the Safety and Effectiveness of ALLEVYN Gentle Border | Number: ALLEV.PMCF.2017.13 |
| | Version: 3.0 |
| | Date: 21 JUN 2019 |
| | Page: Page 63 of 90 |

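### Sections 7.8.1 and 9.1.1 keep subjects stopped for safety or non-compliance in follow-up to day 28, but 9.1.8 and Table 1 can exit them and 12.1.1 closes their adverse event window

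*Combined protocol and SAP*

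**What the plan says.** Two sets of passages in the current protocol (version 3.0) deal with the same subjects.

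**Stay in the study.** Section 7.8.1 is headed as withdrawal from treatment. Its reasons include adverse events, adverse device effects and "Non-compliance (e.g. did not follow instructions"). It says that "the subjects will be followed up to the end of the study for safety assessments until day 28" (±3 days). Section 9.1.1 says of anyone taken off the dressing before Visit 5 that "this subject is still regarded as an active study participant", and asks for continued attendance to Visit 5 for safety. Section 9.1.3 repeats that such subjects attend to give safety information.

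**Leave the study.** Section 9.1.8 defines discontinued subjects to include those "who are withdrawn from the study for reasons of safety or non-compliance". It allows withdrawal from the study when, in the investigator's opinion, "their continued participation in the study poses a risk to the subject, as outlined in section 7.8.1". It adds that, where possible, "the Treatment Discontinuation CRF should be completed for all subjects who discontinue the study early". In the Synopsis, Table 1 ticks the row "End of Study /Exit Form" both at Visit 5 and in the column for treatment discontinuation before the end of study. Table 4 in 21.1.4 carries the same tick.

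**Event window.** Section 12.1.1 defines an adverse event as one arising from enrolment up to treatment discontinuation, not up to day 28 or study exit.

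**The concern.** The same event, for example stopping the dressing because of a device effect, gives a subject two different statuses depending on which section the site reads. Under 7.8.1 and 9.1.1 the subject keeps attending. Under 9.1.8 and the Table 1 tick, the site has grounds to complete the exit form and schedule nothing more.

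Safety is a stated purpose in 4.2, and 4.3.2 says there is as yet no direct clinical evidence on the safety of the dressing with the new wound contact layer. In a single-arm study of 40, scheduled observation after stopping is the main route by which a new event in a subject already stopped for safety would come to light. The event definition adds a second gap: even a site that keeps the subject to day 28 can conclude that a new event at those visits is not an adverse event under the protocol.

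**Working it through.** No figure in the plan rests on this point, so the check is mainly a comparison of passages.

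**1. Are the reasons the same?** 7.8.1 lists adverse event, adverse device effect and non-compliance. 9.1.8 gives safety and non-compliance. They overlap.

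**2. Could 9.1.8 be a separate category of study withdrawal?** It gives no criterion that would separate a safety stop of treatment from a safety exit from the study. It refers to 7.8.1 as its basis and uses the form that 7.8.1 assigns to withdrawal from treatment. The overlap therefore stays.

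**3. What differs for one subject?** Take a subject stopped for a device effect at Visit 2 (day 7, chosen only as an example).

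| | 7.8.1 and 9.1.1 | 9.1.8 and Table 1 |
|---|---|---|
| Status | Active participant | Discontinued from study |
| Remaining key visits | 3 (days 14, 21, 28) | 0 |
| Remaining scheduled observation | 28 − 7 = 21 days | 0 days |
| Share of the 28 days observed | 28/28 = 100% | 7/28 = 25% |

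**4. Does keeping the subject secure the safety data?** Not fully. Under 12.1.1 the window closes at day 7 for this subject, so a new event at day 14, 21 or 28 is outside the definition. For a subject treated to Visit 5 there is no conflict, because the end of treatment and day 28 coincide. The gap affects only those stopped early.

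**5. What is still covered on either reading?** 12.5 recommends a follow-up visit for unresolved events at completion or early discontinuation. 12.5.1 follows related ongoing events until they resolve or become chronic, and unrelated ones for up to 30 days. What is at risk is scheduled detection of new events, not follow-up of known ones.

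**6. Does keeping the subject secure day-28 wound area?** No. The primary endpoint comes from the wound photographs (9.2.3). Section 9.1.3 makes photographs unnecessary at Visits 2 to 4 after an earlier withdrawal from treatment, and 9.1.5 waives the full wound assessment at day 28. Table 1 does tick wound assessment and wound photograph at treatment discontinuation, so area is planned at the stop itself but not assured afterwards.

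**7. Power.** The plan's figures reproduce with a two-sided 5% one-sample t-test and standardised effect 3/5 = 0.6. For n = 26 the noncentrality is 0.6 × √26 = 3.06 and power is 83.6% (stated 83%). For n = 35 it is 0.6 × √35 = 3.55 and power is 93.2% (stated 93%). After the planned 15% loss, 40 × 0.85 = 34 subjects give 92.4%. The documents do not say how many subjects would leave under 9.1.8, so no reduction from these figures can be derived.

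**The case against.** The strongest reply is that this is loose wording with little consequence. Sections 7.8.1, 9.1.1 and 9.1.3 all say subjects continue, and 9.1.5 assumes that treatment-withdrawn subjects attend day 28. Section 9.1.8 says only that subjects may be withdrawn. A ticked form is not a rule ending visits, and ongoing events are followed in any case. All of this stands. It makes the loss a possibility and not a certainty, but it does not tell a site which section governs, and it does not touch the window in 12.1.1.

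Several stronger readings are tempting, and the documents do not support them:

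- *Follow-up is lost in those doing worst, so the day-28 result is biased favourably.* Non-compliance is not a poor wound outcome, and 7.8.1 also lists wound closure as a reason to stop, so early stops include some of the best outcomes. Because of the waivers in 9.1.3 and 9.1.5, day-28 area is not assured even for subjects who stay.
- *Power falls.* Any number of extra exits would be an assumption. The planned analysis is a repeated-measures model in a population needing only one post-baseline assessment (10.2, 10.4.1), so early stoppers can still contribute.
- *One form for two statuses means they cannot be told apart.* The CRFs are not in the documents. Reasons for withdrawal, the separate Study Completion CRF in 9.1.5 and later visit records may separate them. The plan simply does not say so.
- *Section 18 ends follow-up for stopped subjects.* Its wording, "the last visit of the last subject undergoing treatment in the study", defines the end of the whole study. It is not a rule for an individual subject's exit.

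**Conclusion.** The contradiction is real and stands in current text. Sections 7.8.1 and 9.1.1 cannot be applied together with 9.1.8 and the Table 1 tick to a subject stopped for safety or non-compliance, and 12.1.1 does not match the follow-up that 7.8.1 requires. The consequence is limited to a possible loss of scheduled detection of new safety events between the stop and day 28. For a given subject its size depends on the day of stopping. The example in the working assumes a stop at day 7 and a site that acts on 9.1.8. The number of subjects affected and the direction of any effect on wound area are unknown, and no loss of power is claimed. The correction is worth making because safety is a stated purpose and the visits are already required.

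**What to change.** Reconcile 7.8.1, 9.1.1, 9.1.8, Tables 1 and 4, and 12.1.1:

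- **Status.** Define treatment discontinuation and study exit as separate statuses with separate records, and state which data are collected after each.
- **Forms.** Keep the Treatment Discontinuation CRF for stopping treatment. Complete the exit form at Visit 5 or at actual study exit, and remove its tick from the treatment discontinuation column in both tables.
- **Event window.** Make adverse event collection in 12.1.1 match the day-28 safety follow-up in 7.8.1 and 9.1.1.
- **Grounds in 9.1.8.** State explicitly which status follows from risk in continued participation and from missing Visit 1 patient scores. These are existing grounds and should not disappear in the edit. The clinical rule is for the sponsor and investigators to settle, and this review does not choose it.

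These changes would not by themselves recover day-28 wound area after treatment stops. If that is wanted, the waivers in 9.1.3 and 9.1.5 must also be revisited. The handling of missing area, which 10.1 defers to the SAP, should be stated in either case.

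The cost is protocol wording, one schedule tick (shown in two tables), a site memo, and somewhat more adverse event recording at visits already required. No new visits are needed.

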7.2 INCLUSION CRITERIA

Subjects will be considered qualified for enrollment if they meet the following criteria:

| |
|---|
| 
 1. Signed written informed consent. 2. 18 years of age or older. 3. Willing and able to make all required study visits. 4. Able to follow instructions and deemed capable of completing the CWIS questionnaire, Patient Assessment Scale and Pain Scale. 5. Presence of a moderately to highly exuding wound of at least 3cm² in size. 6. Presence of a chronic wound of at least 6 weeks duration at the point of enrollment; full-thickness, partial thickness or shallow granulating wounds. 7. Chronic wounds include: |
|---|

CONFIDENTIAL AND PROPRIETARY

This document contains information that is confidential and proprietary to Smith & Nephew PLC and Smith & Nephew, Inc. and is intended for use only by Smith & Nephew and its manufacturer. It shall not be reproduced or copied in whole or in part, nor shall the contents be disclosed by any means without prior written permission from Smith & Nephew, nor shall anyone make any use of it that is contrary to the expressed or implied wishes of Smith & Nephew.

| | |
|--|---|
| Study Protocol—Device |  |
| A Prospective, Multi-center, Post-Market Clinical Follow-Up Study to Evaluate the Safety and Effectiveness of ALLEVYN Gentle Border | Number: ALLEV.PMCF.2017.13 |
| | Version: 3.0 |
| | Date: 21 JUN 2019 |
| | Page: Page 29 of 90 |

- pressure ulcers or
 - leg ulcers or
 - diabetic foot ulcers.
- or
- Presence of **an acute wound** at the point of enrolment; full-thickness, partial thickness or shallow granulating wounds.
8. Acute wounds include:
- dehisced surgical or
 - traumatic wounds.
9. The patient has a wound size which can be treated with the available sizes and shapes of ALLEVYN Gentle Border. Cutting of the dressing is allowed, if needed. ALLEVYN Gentle Border can be cut and an aseptic technique should be used with cutting the dressing. Ensure any exposed foam areas are covered with an appropriate film dressing taking care not to cover the entire dressing.

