7.6 ENROLMENT

The point of enrolment into the study is when the subject has signed and dated the informed consent document and met all the eligibility criteria.

The anticipated enrolment period for 40 subjects is thirteen (13) months. Once the subject is enrolled a subject ID number will be assigned as a unique study identifier.

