9.1.2 Study Visit 1 - Initial Visit (Baseline Visit, day 0)

The following assessment will be performed at Visit 1.

1. Obtain written informed consent from the subject as detailed in Section 7.5.

----- Do not proceed until consent has been obtained -----
2. Screen the subject for protocol inclusion/exclusion criteria and identify the study wound as the "reference wound" (if more chronic wounds are present per subject).
3. Assign the subject to a study number.
4. Provide the subject with the pages of CWIS and Patient Pain Scale, and allow sufficient time to complete it.
5. Classify the wound type and perform wound assessment according to the Bates-Jensen Wound Assessment Tool (BWAT), as outlined in chapter 9.2.4.
6. **Photograph the wound** with the delivered digital camera (Silhouette) and make sure that the image is assigned to the correct patient.
7. Apply ALLEVYN Gentle Border dressing on the wound.
8. Record details of the size and order number of ALLEVYN Gentle Border (including dressing cut, if performed). ALLEVYN Gentle Border can be cut and an aseptic technique should be used with cutting the dressing. Ensure any exposed foam areas are covered with an appropriate film dressing taking care not to cover the entire dressing.
9. Assess the ease of applying the dressing, including remains in place and repositioning (if applicable).
10. Instruct the subject to carefully follow the standard care instructions until the next dressing change and provide information concerning arrangements for future study visits. Subjects should return to the study center for the next study visit in 7 days (± 3), or earlier if a dressing change is required.

CONFIDENTIAL AND PROPRIETARY

This document contains information that is confidential and proprietary to Smith & Nephew PLC and Smith & Nephew, Inc. and is intended for use only by Smith & Nephew and its manufacturer. It shall not be reproduced or copied in whole or in part, nor shall the contents be disclosed by any means without prior written permission from Smith & Nephew, nor shall anyone make any use of it that is contrary to the expressed or implied wishes of Smith & Nephew.

| | |
|--|---|
| Study Protocol—Device |  |
| A Prospective, Multi-center, Post-Market Clinical Follow-Up Study to Evaluate the Safety and Effectiveness of ALLEVYN Gentle Border | Number: ALLEV.PMCF.2017.13 |
| | Version: 3.0 |
| | Date: 21 JUN 2019 |
| | Page: Page 36 of 90 |

- | |
|---|

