9.2.6 Patient Pain Scale (PPS)

During the AGB treatment phase, the patient will be asked to describe the level of pain during the application, during AGB treatment and on removal of the dressing on a scale from 0 (no pain) to 10 (worst pain). The subject will be asked to draw a vertical line on this visual scale to indicate the value. The value will be rounded to a whole number and transmitted into the CRF by the investigator. The PPS will be entered directly into the case report form and will serve as source data.

CONFIDENTIAL AND PROPRIETARY

[figure not shown]
This document contains information that is confidential and proprietary to Smith & Nephew PLC and Smith & Nephew, Inc. and is intended for use only by Smith & Nephew and its manufacturer. It shall not be reproduced or copied in whole or in part, nor shall the contents be disclosed by any means without prior written permission from Smith & Nephew, nor shall anyone make any use of it that is contrary to the expressed or implied wishes of Smith & Nephew.

| | |
|--|---|
| Study Protocol—Device |  |
| A Prospective, Multi-center, Post-Market Clinical Follow-Up Study to Evaluate the Safety and Effectiveness of ALLEVYN Gentle Border | Number: ALLEV.PMCF.2017.13 |
| | Version: 3.0 |
| | Date: 21 JUN 2019 |
| | Page: Page 46 of 90 |

[figure not shown]
Level of pain experienced by the subject on application of the dressing

Level of pain experienced by the subject during treatment with AGB

Level of pain experienced by the subject on removal of the dressing

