10.2 ANALYSIS POPULATIONS

The following analysis populations will be used for this study:

- **Safety Population (SAF):** Including all subjects who enroll in the study and receive the study treatment. This population will be used for analysis of safety.
- **Modified Intention to Treat population (mITT):** following Intention to Treat principle including all subjects who are enrolled into the study and complete at least one post-baseline assessment. This population will be used for the primary analysis of the primary and secondary endpoints.

CONFIDENTIAL AND PROPRIETARY

This document contains information that is confidential and proprietary to Smith & Nephew PLC and Smith & Nephew, Inc. and is intended for use only by Smith & Nephew and its manufacturer. It shall not be reproduced or copied in whole or in part, nor shall the contents be disclosed by any means without prior written permission from Smith & Nephew, nor shall anyone make any use of it that is contrary to the expressed or implied wishes of Smith & Nephew.

| | |
|--|---|
| Study Protocol—Device |  |
| A Prospective, Multi-center, Post-Market Clinical Follow-Up Study to Evaluate the Safety and Effectiveness of ALLEVYN Gentle Border | Number: ALLEV.PMCF.2017.13 |
| | Version: 3.0 |
| | Date: 21 JUN 2019 |
| | Page: Page 49 of 90 |

- **Per-Protocol Population (PP):** including all subjects in the mITT, who have no significant protocol deviations and who meet the inclusion/exclusion criteria. This population will be used for a secondary analysis of the primary and secondary endpoints.

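### Section 9.1.8 lets an enrolled, eligible subject be withdrawn from the whole study over incomplete Visit 1 questionnaires, although the primary wound-area endpoint does not need them

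*Combined protocol and SAP*

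**What the plan says.** Section 9.1.8 (Discontinued Subjects) includes subjects "withdrawn from the study for failure to complete the patient scores at Visit 1". The wording is withdrawal from the study, not from the dressing and not from the questionnaire analysis. Other sections bear on what follows.

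- **Enrolment (7.6).** "The point of enrolment into the study is when the subject has signed and dated the informed consent document and met all the eligibility criteria".
- **Eligibility (7.2, criterion 4).** "Able to follow instructions and deemed capable of completing the CWIS questionnaire, Patient Assessment Scale and Pain Scale". This concerns judged capability, not actual completion.
- **Visit 1 order (9.1.2).** The study number is assigned at step 3. Step 4 reads "Provide the subject with the pages of CWIS and Patient Pain Scale, and allow sufficient time to complete it". The baseline wound photograph is step 6, and step 7 reads "Apply ALLEVYN Gentle Border dressing on the wound".
- **Endpoints (8.2.1, 8.2.2, 9.2.3).** The primary endpoint is absolute reduction in wound area, taken from the Silhouette photographs. CWIS and pain are secondary.
- **Analysis sets (10.2).** The mITT takes those "enrolled into the study and complete at least one post-baseline assessment". The safety population requires that study treatment was received.
- **Withdrawal from treatment (7.8.1, 9.1.1).** These subjects remain active participants and are followed for safety up to visit 5.
- **Replacement (7.8.1).** After the rule on failing the minimum wound size, the text says "Subjects withdrawn from the study for this reason alone shall be replaced by enrolment of a new study subject". No replacement is stated for missing scores.

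**The concern.** The clause links retention for the primary endpoint to completion of a secondary instrument. The area model in section 10.4.1 always contains visit and may add centre, wound type, BMI and baseline area. None of these comes from a questionnaire. An eligible subject whose wound could be imaged at every visit can therefore be lost to the primary analysis because a form was left incomplete. Section 10.1 already leaves missing data to the SAP, where a missing baseline score could be handled within its own analysis.

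The clause also sits awkwardly with the rest of the plan. A subject taken off the dressing, even for non-compliance, stays in the study and is followed. A subject with an incomplete form can leave altogether.

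The trigger is unclear as well, because the term used for the Visit 1 scores is not defined. The Visit 1 set includes the Pain Scale, which section 9.2.6 describes as rating pain "during the application, during AGB treatment and on removal of the dressing". At step 4 no study dressing has been applied, so at least the rating for the treatment period cannot yet be made. Sites could reasonably apply the clause differently.

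At stake are some primary-endpoint data, some precision and, in one branch of the Visit 1 sequence, safety follow-up.

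**Working it through.** **Step 1: where the withdrawal falls.** Enrolment (7.6) and numbering (9.1.2, step 3) come before the questionnaires (step 4). The withdrawal is therefore post-enrolment. Two branches follow.

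- *Stopped at step 4, before the dressing.* There is no exposure, so the subject is not in the safety population and has no on-treatment safety data to lose. There is no later area measurement, so the subject is not in the mITT.
- *Stopped after the dressing is applied.* This can happen if a site waits for the application-pain rating. The subject is in the safety population by definition. Later area data are not collected, and follow-up to visit 5 is not provided as it is after treatment withdrawal.

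**Step 2: reproduce the plan's power.** Inputs are a mean reduction of 3 cm² and SD of 5 cm² (Synopsis; section 11) and two-sided alpha of 0.05 (10.1). The method is a one-sample t-test with noncentrality δ = (3/5)√n and

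power = 1 − F(t; n−1, δ) + F(−t; n−1, δ),

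where F is the noncentral t distribution function and t is the 0.975 quantile of the central t on n−1 degrees of freedom.

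- n = 26: δ = 0.6 × √26 = 3.06, power 83.6% (plan: 83%).
- n = 35: δ = 0.6 × √35 = 3.55, power 93.2% (plan: 93%).

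Both stated figures reproduce.

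**Step 3: effect of unreplaced Visit 1 withdrawals.** The documents give no rate of incomplete forms. Assume 5% to 10% of 40, that is 2 to 4 subjects, followed by the plan's 15% loss, rounding down. The half-width is t × 5/√n.

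| Withdrawn at Visit 1 | Evaluable n | Power | 95% CI half-width |
|---|---|---|---|
| 0 | 40 × 0.85 = 34 | 92.4% | 1.74 cm² |
| 2 | 38 × 0.85 = 32.3, so 32 | 90.8% | 1.80 cm² |
| 4 | 36 × 0.85 = 30.6, so 30 | 88.8% | 1.87 cm² |

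**Step 4: the separate V3.0 analysis.** Section 11 plans a separate analysis of subjects who comply with V3.0, aiming for more than 80% power, and states that 10 subjects were enrolled under V2.0. Assume this set is exactly the remaining 40 − 10 = 30, all compliant, with 15% loss. With no Visit 1 withdrawals, 30 × 0.85 = 25.5, so n = 25 and power is 82.1%. One withdrawal gives n = 24 and 80.4%; two give n = 23 and 78.5%. The margin here is thin to begin with, and any V2.0 subject who also meets V3.0 would add to it.

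**The case against.** The strongest case on the other side is that section 9.1.8 defines who counts as discontinued. It does not order that every incomplete form end participation, and the Visit 1 instructions contain no withdrawal step. Completion is also linked to eligibility: a subject who cannot finish the forms casts doubt on criterion 4, usually before exposure. Whole-study power stays above the original 83% design even with four such losses.

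Much of this stands. The clause permits the withdrawal; it does not clearly compel it. Its absence from the reasons in section 7.8.1 proves little, because that list is open-ended and concerns treatment. The power effect is modest. Still, being judged capable differs from having completed a form, and none of these arguments gives a reason to remove an eligible subject from the area analysis.

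Three stronger readings are tempting, but the documents do not support them.

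- *That wound-area or safety data already collected are discarded.* No text says so. Section 7.8.3 allows use of data up to withdrawal, though only for withdrawal of consent. What stops is future collection.
- *That safety information is generally lost.* Before application there is none on treatment. After it, section 9.1.8 asks for the discontinuation form where possible, the schedule's discontinuation column includes adverse events, device deficiencies and a wound photograph, and section 12.5 covers follow-up of ongoing events. The gap is the missing planned follow-up to visit 5.
- *That the result shifts toward easier wounds.* Frailer patients may leave more forms incomplete, but nothing in the documents links completion to healing. The endpoint is absolute cm², which also depends on baseline size, so even the direction is open.

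**Conclusion.** The point holds in a limited form. Section 9.1.8 allows an enrolled, eligible subject to leave the study for an incomplete secondary score, with loss of post-baseline area data and of mITT membership, and with no stated replacement. Where the dressing has already been applied, follow-up also falls short of what sections 7.8.1 and 9.1.1 give after treatment withdrawal.

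The loss of power (1.6 to 3.6 percentage points) and the wider interval (0.06 to 0.13 cm² more on each side) rest on an assumed 2 to 4 affected subjects and on the plan's own 3 and 5 cm² assumptions. The true rate could be zero. Selection bias can be neither signed nor sized from the documents. This is a cheap improvement worth making, not a threat to the study's validity.

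**What to change.** Delete from section 9.1.8 the category of subjects "withdrawn from the study for failure to complete the patient scores at Visit 1". In its place, state that an otherwise eligible subject with an incomplete baseline CWIS or Pain Scale stays in the study and is imaged and followed at all visits. That subject is included in the safety population and the mITT whenever the section 10.2 definitions are met, and is treated as missing only in the affected change-from-baseline patient-reported analysis. Inclusion must be conditional, because the safety population requires treatment and the mITT requires an assessment after baseline.

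Reconcile sections 7.8.1, 9.1.1 and 9.1.8 so that withdrawal from treatment and withdrawal from the study are kept apart. The clinical reasons for stopping the dressing are not affected.

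The cost is a sentence or two of protocol text. The downside is that the CWIS change analysis may have a slightly smaller n than the area analysis.
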